3.4.4 Observational Endpoint[s]

Not applicable for SMT analysis

3.4.5 Sensitivity analysis due to COVID-19 pandemic

Not applicable for SMT analysis

3.4.6 Handling of Missing Data and Outliers

3.4.6.1 Safety

3.4.6.1.1 Immediate

For unsolicited systemic AEs, a missing response to the “Immediate” field is assumed to have occurred after the 30-minute surveillance period and will not be imputed.

3.4.6.1.2 Causal Relationship

By convention, all events reported at the injection site (either solicited or unsolicited) will be considered as related to the administered product and then referred to as reactions. In a same way, all solicited systemic events pre-listed in the CRF are also considered as related to vaccination and will be considered as reactions.

- For unsolicited systemic AE, missing relationship to IMP will be considered as related to study vaccines³ at the time of analysis.
- The missing relationship to study procedures for SAEs will not be imputed.

3.4.6.1.3 Intensity

For solicited reactions, missing intensities will be handled as described in [Section 4.2.1.1.1](#). For unsolicited AEs, missing intensities will remain missing and will not be imputed.

3.4.6.1.4 Start Date and End Date

Missing or partially missing start dates or end dates for unsolicited AEs (including SAEs) will remain missing and not be imputed. If the start date is missing or partially missing, the time of onset will be considered to be missing. Nevertheless, unsolicited AEs with missing time of onset will be included in analyses according to the last vaccination (computed according to the section [4.2.1.2.3](#)). If either the start date or end date is missing or partially missing, the duration will be considered missing.

Missing or partially missing end dates for ongoing solicited AEs will remain missing and not be imputed.

3.4.6.1.5 Action Taken

Missing actions taken will remain missing and not be imputed.

3.4.6.2 Immunogenicity

Not applicable.

3.5 Interim Analysis

This study will not include an early safety data review. However, participant safety will be continuously monitored by the Sponsor's internal safety review committee which includes safety signal detection at any time during the study.

No analyses are planned to be performed prior to the formal completion of the study.

3.6 Data Monitoring Committee (DMC)

Not applicable.

³ A study vaccine is any vaccine that is administered as part of the study, including the meningococcal vaccines (MenACYW conjugate vaccine and Nimenrix), and the concomitant vaccines (Tdap-IPV and 9vHPV).

4 Complementary Information on Assessment Methods

Study assessments and procedures are detailed in Section 8 of the protocol. This section focusses on complementary/additional information not detailed in the protocol.

4.1 Complementary Information for Endpoints Assessment Methods

Not applicable.

4.2 Complementary Information on Derived Endpoints: Calculation Methods

4.2.1 Safety

4.2.1.1 Solicited Reactions

4.2.1.1.1 Daily Intensity

All daily records for solicited reactions will be derived into daily intensity according to the following classification: None, Grade 1, Grade 2, Grade 3, or Missing (Unknown).

For the derivation of daily intensities, the following sequential steps will be applied:

- 1) Solicited reactions (except Fever/Pyrexia) with CRF presence recorded as “No” and with all daily records missing (Unknown) then all daily intensities will be derived as None.
- 2) For non-measurable solicited reactions, daily intensities will correspond to daily records reported in the clinical database. For measurable solicited reactions the daily measurements reported in the clinical database will be converted based upon the intensity scales defined in the protocol; this assumes a reaction that is too large to measure (non-measurable, “NM”) is Grade 3. Note the intensity could be considered “None” (not a reaction) in the analysis despite being considered a reaction by the investigator (e.g., swelling measurement > 0 mm but < 25 mm in adults).

Note: The maximum intensity on the ongoing period is derived from the record of the maximum intensity/measurement after the end of the solicited period following the rule described above.

Table 4.1: Solicited injection site reactions: terminology, definitions, and intensity scales – Adolescents aged ≥ 10 to <17 years

CRF term (MedDRA LLT)	Injection site pain	Injection site erythema	Injection site swelling
Diary card term	Pain	Redness	Swelling

Definition	Pain either present spontaneously or when the injection site is touched or injected limb is mobilized	Presence of a redness including the approximate point of needle entry	Swelling at or near the injection site Swelling or edema is caused by a fluid infiltration in tissue or cavity and, depending on the space available for the fluid to disperse, swelling may be either soft (typically) or firm (less typical) to touch and thus can be best described by looking at the size of the swelling
Intensity scale*	
CRF: Grade 1: A type of adverse event that is usually transient and may require only minimal treatment or therapeutic intervention. The event does not generally interfere with usual activities of daily living. Grade 2: A type of adverse event that is usually alleviated with additional therapeutic intervention. The event interferes with usual activities of daily living, causing discomfort but poses no significant or permanent risk of harm to the research participant. Grade 3: A type of adverse event that interrupts usual activities of daily living, or significantly affects clinical status, or may require intensive therapeutic intervention.
 
Diary card: Grade 1: No interference with usual activities Grade 2: Some interference with usual activities Grade 3: Significant; prevents usual activities
	Grade 1: ≥ 25 to ≤ 50 mm Grade 2: ≥ 51 to ≤ 100 mm Grade 3: > 100 mm	Grade 1: ≥ 25 to ≤ 50 mm Grade 2: ≥ 51 to ≤ 100 mm Grade 3: > 100 mm

LLT: lowest level term; MedDRA: Medical Dictionary for Regulatory Activities.

* For the subjective reaction of pain, participants or parents/legally acceptable representatives will record the intensity level (Grade 1, 2, or 3) in the diary card. For the measurable reactions of redness and swelling, they will record just the size of the reaction, and the classification as Grade 1, 2, or 3 will be assigned at the time of the statistical analysis.

Table 4.2: Solicited systemic reactions: terminology, definitions, and intensity scales – Adolescents aged ≥ 10 to < 17 years

CRF term (MedDRA LLT)	Fever	Headache	Malaise	Myalgia
Diary card term	Temperature	Headache	Feeling unwell	Muscle aches and pains
Definition	Elevation of temperature to $\geq 38.0^{\circ}\text{C}$ ($\geq 100.4^{\circ}\text{F}$)	Pain or discomfort in the head or scalp. Does not include migraine.	General ill feeling. Malaise is a generalized feeling of discomfort, illness, or lack of well-being that can be associated with a disease state. It can be accompanied by a sensation of exhaustion or inadequate energy to accomplish usual activities.	Muscle aches and pains are common and can involve more than one muscle at the same time. Muscle pain can also involve the soft tissues that surround muscles. These structures, which are often referred to as connective tissues, include ligaments, tendons, and fascia (thick bands of tendons). Does not apply to muscle pain at the injection site which should be reported as injection site pain.
Intensity scale*	Grade 1: $\geq 38.0^{\circ}\text{C}$ to $\leq 38.4^{\circ}\text{C}$, or $\geq 100.4^{\circ}\text{F}$ to $\leq 101.1^{\circ}\text{F}$	CRF: Grade 1: A type of adverse event that is usually transient and may require only minimal treatment or therapeutic intervention. The event does not generally interfere with usual activities of daily living.	CRF: Grade 1: A type of adverse event that is usually transient and may require only minimal treatment or therapeutic intervention. The event does not generally interfere with usual activities of daily living.	CRF: Grade 1: A type of adverse event that is usually transient and may require only minimal treatment or therapeutic intervention. The event does not generally interfere with usual activities of daily living.

CRF term (MedDRA LLT)	Fever	Headache	Malaise	Myalgia
	Grade 2: $\geq 38.5^{\circ}\text{C}$ to $\leq 38.9^{\circ}\text{C}$, or $\geq 101.2^{\circ}\text{F}$ to $\leq 102.0^{\circ}\text{F}$	Grade 2: A type of adverse event that is usually alleviated with additional therapeutic intervention. The event interferes with usual activities of daily living, causing discomfort but poses no significant or permanent risk of harm to the research participant.	Grade 2: A type of adverse event that is usually alleviated with additional therapeutic intervention. The event interferes with usual activities of daily living, causing discomfort but poses no significant or permanent risk of harm to the research participant.	Grade 2: A type of adverse event that is usually alleviated with additional therapeutic intervention. The event interferes with usual activities of daily living, causing discomfort but poses no significant or permanent risk of harm to the research participant.
	Grade 3: $\geq 39.0^{\circ}\text{C}$ or $\geq 102.1^{\circ}\text{F}$	Grade 3: A type of adverse event that interrupts usual activities of daily living, or significantly affects clinical status, or may require intensive therapeutic intervention. Diary card: Grade 1: No interference with usual activities Grade 2: Some interference with usual activities Grade 3: Significant; prevents usual activities	Grade 3: A type of adverse event that interrupts usual activities of daily living, or significantly affects clinical status, or may require intensive therapeutic intervention. Diary card: Grade 1: No interference with usual activities Grade 2: Some interference with usual activities Grade 3: Significant; prevents usual activities	Grade 3: A type of adverse event that interrupts usual activities of daily living, or significantly affects clinical status, or may require intensive therapeutic intervention. Diary card: Grade 1: No interference with usual activities Grade 2: Some interference with usual activities Grade 3: Significant; prevents usual activities

LLT: lowest level term; MedDRA: Medical Dictionary for Regulatory Activities

* For all reactions but fever, participants or parents/legally acceptable representatives will record the intensity level (Grade 1, 2, or 3) in the diary card. For fever, they will record the body temperature, and the classification as Grade 1, 2, or 3 will be assigned at the time of the statistical analysis based on the unit used to measure the temperature and the intensity scale.

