4.2.1.1.2 Maximum Intensity

Maximum overall intensity is derived from the daily intensities computed as described in Section 4.2.1.1.1 and is calculated as the maximum of the daily intensities over the period considered.

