4.2.1.1.3 Presence

Presence is derived from the maximum overall intensity over the time period considered:

- None: No presence

- Grade 1, Grade 2, or Grade 3: Presence
- Missing or Unknown: Missing presence

Participants with at least one non-missing presence for a specific endpoint will be included in the analysis. Conversely, those without a non-missing presence will not be included in the analysis of the endpoint.

The time period is displayed as D1-D4, D5-D8, D9 and later.

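### For pain, headache, malaise and myalgia, the SAP keeps a CRF 'No' with no daily records as a non-case but drops a CRF 'Yes' with no daily records, so the any-grade rate leans low.

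*SAP*

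**What the plan says.** SAP 4.2.1.1.1 derives daily intensities in two steps.

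- **Step 1** covers all solicited reactions except fever. It applies to a reaction with "CRF presence recorded as “No” and with all daily records missing (Unknown) then all daily intensities will be derived as None".
- **Step 2** takes everything else from the daily data. The rule for pain, headache, malaise and myalgia reads: "For non-measurable solicited reactions, daily intensities will correspond to daily records reported in the clinical database". Redness, swelling and fever are instead graded from each day's measurement on the protocol's scales.

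SAP 4.2.1.1.2 defines the maximum overall intensity, which "is calculated as the maximum of the daily intensities over the period considered". In SAP 4.2.1.1.3, "Presence is derived from the maximum overall intensity over the time period considered": a missing maximum gives a missing presence. On participants in that position the section says: "Conversely, those without a non-missing presence will not be included in the analysis of the endpoint".

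The missing-data section adds no further rule. Its sentence in SAP 3.4.6.1.3, which begins "For solicited reactions, missing intensities will be handled as described in", only points the reader back to the daily-intensity section.

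**The concern.** The CRF presence answer settles a participant's status when it is 'No' and is ignored when it is 'Yes'. For a non-measurable reaction, a 'Yes' already answers whether a reaction of any grade occurred; only the grade and the days are unknown. Under the written rules this known reaction is removed, while a participant with equally empty daily fields and a 'No' stays in as a non-case. Inclusion in the denominator then depends on the outcome.

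Solicited reactions from the day of vaccination through 7 days are a named endpoint of the safety objective, and by the SAP's own convention all of them count as related to vaccination. What is at stake is whether the any-grade percentages leave out reactions that the site recorded as having happened. The Clopper-Pearson intervals would not show the omission, because they are computed on the reduced counts.

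The treatment also differs from how the SAP handles unsolicited events with missing attributes. A missing relationship is counted as related (3.4.6.1.2). A missing onset is kept within the 30-day tables (4.2.1.2.4). An unsolicited event that caused discontinuation counts even if its grade is missing (4.2.2.6).

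**Working it through.** The documents state no reactogenicity rate and no rate of missing diary data, so there is no plan figure to reproduce. The check is a trace of the rules followed by the arithmetic they imply.

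**Inputs.** Derivation rules: SAP 4.2.1.1.1 to 4.2.1.1.3. Group sizes: SAP Table 1.1, with 174 planned in each of Groups 1 and 2 and 116 in Group 3. Groups 1 and 2 are pooled in SAP 3.4.3, so N = 174 + 174 = 348. Assumed, because the documents do not give them: the true number of cases c, and the number k of participants with CRF 'Yes' and all daily records missing.

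**Trace with all eight solicited days missing.**

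| Reaction | CRF presence | Daily intensity | Presence | Result |
|---|---|---|---|---|
| Not fever | No | None (step 1) | No presence | kept as non-case |
| Not fever | Yes | Missing (step 2 has nothing to convert) | Missing | excluded |
| Fever | No | Missing (exempt from step 1) | Missing | excluded |
| Fever | Yes | Missing | Missing | excluded |

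The asymmetry exists for non-fever reactions. Fever is treated alike in both cases.

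**Effect for pain, headache, malaise and myalgia.** Each of the k excluded participants is a case.

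- Full rate: c/N.
- Rate under the SAP: (c-k)/(N-k).
- Difference: (c-k)/(N-k) - c/N = -k(N-c)/[N(N-k)].

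This is negative whenever k > 0 and c < N.

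| N | assumed c (rate) | assumed k | SAP rate | shift, points |
|---|---|---|---|---|
| 348 | 174 (50.0%) | 1 | 173/347 = 49.9% | -0.14 |
| 348 | 174 (50.0%) | 9 | 165/339 = 48.7% | -1.33 |
| 348 | 174 (50.0%) | 17 | 157/331 = 47.4% | -2.57 |
| 348 | 104 (29.9%) | 1 | 103/347 = 29.7% | -0.20 |
| 348 | 104 (29.9%) | 7 | 97/341 = 28.4% | -1.44 |
| 116 | 58 (50.0%) | 1 | 57/115 = 49.6% | -0.43 |
| 116 | 58 (50.0%) | 6 | 52/110 = 47.3% | -2.73 |

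For scale, the 95% Clopper-Pearson interval for 173/347 is 44.5% to 55.2%, so a single excluded case is far inside sampling error.

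**Redness and swelling.** A 'Yes' may be a reaction under 25 mm, which SAP 4.2.1.1.1 scores as None. Let s be the SAP rate and q the share of the k excluded 'Yes' participants who were at or above 25 mm. The full rate minus the SAP rate is k(q-s)/N. The SAP rate is too low only if q > s. With assumed figures of 20 cases among 165 analysed (s = 12.1%), k = 9 and q = 40%, the full rate is (20 + 3.6)/174 = 13.6%. With q below 12.1% the sign reverses.

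**The case against.** The strongest reply is that k should be near zero. Protocol 8.3.2 has the site interview the participant or parent, clarify incomplete diary entries, and report electronically information that was not in the diary. Protocol 10.3.5 requires an intensity grade for every adverse event. A 'Yes' with eight empty days should therefore be rare. This stands as an argument about size. It does not rule the record out, because diaries are collected at the visit 30 days (+14) after vaccination, and a participant may then recall that pain occurred without its daily grades.

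A second reply is that the SAP deliberately builds solicited results from daily records and sets aside the investigator's flag for ongoing status (4.2.1.1.7). The reason given there is that the measurement decides. That does not carry over to four reactions with no measurement, and step 1 itself already relies on the CRF answer. Keeping the 'No' participants is sound, since 'No' is an observed answer; the gap is the absent rule for 'Yes'.

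Third, counting such a participant as a case affects more than one line. Presence is shown by period, solicited onset has no Missing category, and days of presence would come out as zero. This is correct, and the fix must cover those displays.

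A reader might go further in three ways that the documents do not support:

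- **All reactogenicity rates are biased downward.** Fever is symmetric, and for redness and swelling the direction depends on q.
- **A 'Yes' with one day None and the rest missing is turned into a non-case.** That follows only if the maximum is taken over the non-missing days. SAP 4.2.1.1.2 does not say how None and Missing combine, so the outcome is unspecified.
- **A general diary-missing rate of 5% or 10% can be applied to 'Yes' and 'No' alike.** The documents give no such rate. Only 'Yes' records create the bias, and blank days after a 'No' may simply be how the form is completed.

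**Conclusion.** The point holds for pain, headache, malaise and myalgia: as written, a CRF 'Yes' with all daily records missing is excluded while the corresponding 'No' is kept, and any such 'Yes' lowers the any-grade rate. The direction is certain for these four once k is at least 1. The size is not known. It rests on assumed rates and on planned group sizes used as denominators. In pooled Groups 1 and 2 at 50%, the shift runs from about -0.14 points (k = 1) to about -1.3 points (k = 9, or 9/174 = 5.2% of the assumed cases), and the lower end is more likely. If k = 0, nothing changes.

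The check assumes that the CRF presence field can hold 'Yes' without daily entries; the CRF is not among the documents. Differing diary completeness between open-label Group 3 and the blinded groups is conceivable, but nothing in the documents shows it. The analysis in this SAP is descriptive with Groups 1 and 2 pooled, so no hypothesis test and no primary result is affected. This is a minor point, worth correcting because the correction is cheap.

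**What to change.** Amend SAP 4.2.1.1.1 to 4.2.1.1.3 as follows.

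- **Pain, headache, malaise, myalgia:** when CRF presence is 'Yes' and all daily records are missing, derive overall D1-D8 presence as Presence and maximum intensity as Missing. Count the participant in the numerator and denominator of the any-grade rate. Add a Missing category to the intensity, by-period, time-of-onset and days-of-presence displays.
- **Redness and swelling:** keep presence as Missing, and footnote the number of CRF 'Yes' records without a measurement.
- **Fever:** leave as written.
- **'Yes' with only None and missing days:** report the count and do not force presence.

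If the main derivation is to stay unchanged, the minimum is to report k with a sensitivity rate that counts those participants as cases.

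No new data are needed, because step 1 already reads the CRF presence field. The cost is a short programming change, small additions to several tables, and possibly a few participants shown with unknown grade and day.

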4.2.1.1.2 Maximum Intensity

Maximum overall intensity is derived from the daily intensities computed as described in Section 4.2.1.1.1 and is calculated as the maximum of the daily intensities over the period considered.

4.2.1.1.3 Presence

Presence is derived from the maximum overall intensity over the time period considered:

- None: No presence

- Grade 1, Grade 2, or Grade 3: Presence
- Missing or Unknown: Missing presence

Participants with at least one non-missing presence for a specific endpoint will be included in the analysis. Conversely, those without a non-missing presence will not be included in the analysis of the endpoint.

The time period is displayed as D1-D4, D5-D8, D9 and later.

4.2.1.1.4 Time of Onset

Time of onset is derived from the daily intensities computed as described in Section 4.2.1.1.1. It corresponds to the first day with intensity of Grade 1, Grade 2, or Grade 3.

Note: If a reaction is not continuous (i.e., reaction occurs over two separate periods of time intervened by at least one daily intensity Missing or None) then the time of onset is the first day of the first occurrence.

Time of onset period is displayed as, D1-D4, D5-D8.

4.2.1.1.5 Number of Days of Presence During the Solicited Period

Number of days of presence over the period considered is derived from the daily intensities computed as described in Section 4.2.1.1.1. It corresponds to the number of days with daily intensities of Grade 1, Grade 2, or Grade 3.

4.2.1.1.6 Overall Number of Days of Presence

If a reaction is ongoing at the end of the solicited period, then the overall number of days of presence is derived from the daily intensities and the end date of the reaction after the end of the solicited period. The overall number of days of presence is:

- (End date - last vaccination date) + (number of days of presence within the solicited period [8]) - length of the solicited period + 1

If the end date is missing or incomplete (contains missing data), the overall number of days of presence will be considered as Missing.

4.2.1.1.7 Ongoing

Ongoing is derived from the last daily intensity of the solicited period computed as described in Section 4.2.1.1.1 and the maximum intensity on the ongoing period. The investigator's ongoing flag is not used because the measurement would determine the ongoing status of the reaction.

- Ongoing: if the last daily intensity of the solicited period is at least Grade 1 and the maximum intensity on the ongoing period is at least Grade 1
- Not ongoing: if the last daily intensity of the solicited period is None or the maximum intensity on the ongoing period is None.

- Missing: all other conditions (in this case, it is not included in the denominator of the ongoing analysis in the safety tables).

4.2.1.2 Unsolicited AEs

4.2.1.2.1 Presence

An observation will be considered an event if it has at least a verbatim term and is not a Grade 0 intensity event.

Grade 0 events are not included in safety analysis but are included in separate listings.

4.2.1.2.2 Intensity

Intensity will be derived according to the following classification: None, Grade 1, Grade 2, Grade 3, or Missing.

If the unsolicited AE is measurable and its preferred term is part of the list of solicited reactions, then the measurement is derived based upon and following the same rule of the intensity scales defined in [Table 4.1](#) and [Table 4.2](#) for that measurable injection site or systemic reaction. Note the intensity could be considered as “None” (not a reaction) in the analysis despite being considered a reaction by the investigator (e.g., swelling measurement >0 mm but < 25 mm in adults).

Intensity for the other unsolicited AEs will correspond to the value reported in the CRF.

The maximum intensity corresponds to the highest intensity for a unique term.

